C7k) Maternal blood draw: Maternal venous blood will be collected at 5 times through the study (baseline, end of intervention, 2 months, 6 months, and 12 months postpartum) after an overnight fast by a trained phlebotomist. A total of two 4-mL EDTA (lavender top) tubes (1 will be filled ½ full), one 10-mL EDTA, one 7.5-mL serum (tiger top) tube, and one 8.5mL serum tubes will be collected. At the baseline visit and additional one 6-mL ACD (yellow top) plasma vacutainer will be collected for ApoE genotyping. All tubes will be placed on ice and processed within 24 hours, including aliquoting for analysis. All tubes will be appropriately labeled with the study identification number, date (mm/dd/yyyy), and time (24-hour time, hh:mm). Blood samples will be analyzed to assess biomarkers related to cardiometabolic health (including serum lipids, glucose metabolism, and inflammation), gut metabolites (short chain fatty acids) and neuronal health (including assessment of underlying ApoE genetics). Samples will be sent to Quest Diagnostics for cardiometabolic markers (standard lipid panel (total cholesterol, triglycerides, HDL-C, LDL-C (calculated), Cholesterol/HDL ratio (calculated), and non-HDL-C (calculated)), hemoglobin A1C, plasma glucose, serum insulin, and high sensitivity- C-reactive protein). All other samples will be stored at -80°C for analysis. Batched samples will be analyzed at KUMC according to the protocols of the manufacturer using the following formats:, SIMOA (neurofilament-light and inflammatory cytokines), and polymerase chain reaction (ApoE genotype). Unused samples will be banked for future evaluations related to nutrition and brain health including free cell RNA analysis at KUMC.

C7l) Actigraphy: Maternal physical activity and sleep will be monitored using the ActiGraph wG3TX-BT. The device will be worn at the wrist for 7 days around 5/6 study visits (baseline, end of intervention, 2 months, 6 months, and 12 months postpartum). Participants will not be able to view any device data. Participants will also be asked to keep a sleep and activity log during this time. Participants will be mailed the device and given instructions for use prior to each study visit, along with an activity and sleep tracker. Following the 7-day monitoring period, participants will return the device and log back to the study team. Data collected from the device are available at <https://www.actigraphcorp.com/actigraph-wgt3x-bt/> and include raw acceleration, steps, METs, total sleep time, sleep efficiency, and others related to activity and sleep. Participants will download an application on a home device that will allow them to daily sync the activity information via Bluetooth and send it to the cloud-based data management platform <https://actigraphcorp.com/centrepoint/>.

C7m) Maternal vitals: Blood pressure & heart rate will be assessed 6 times throughout the study (baseline, end of intervention, 2 weeks 2 months, 6 months, and 12 months) using the Omron HEM 907XL IntelliSense Professional Digital Blood Pressure Monitor. Participants will be instructed to sit quietly for 5 minutes in the upright position with feet flat on the floor. After completing the period, blood pressure cuff will be placed around

the upper arm and assessment completed per manufacturer's recommendations. The measurement will be repeated until 2 are within 5 mmhg agreement.

C7n) Veggie meter: Maternal carotenoid skin content will be assessed at 5 time points (baseline, end of intervention, 2 months, 6 months, and 12 months) using the veggie meter. Participants will insert a finger into the machine. The machine uses LED light to detect pigments. Three measurements will be taken and averaged, each lasting 10-45 seconds.

C7o) Maternal cognitive testing: The NIH Toolbox Cognition Battery will be used to assess cognitive function in several different domains, including executive function, language, episodic memory, processing speed, and attention 5 times throughout the study (baseline, end of intervention, 2 months, 6 months, and 12 months). The test will be administrated by a trained team member on an Apple iPad. Consistent with the toolbox recommendations, collected data will be emailed to a member of the study team and archived on the P-Drive. The record is not required to be kept on the iPad and can be expunged after confirmation that it has been archived on the P-Drive.

C7p) Maternal olfactory testing: Participant olfaction will be evaluated at 4 times throughout the study (baseline, end of intervention, 2 months, and 12 months). Each patient will be tested with fourteen different scents using aromatherapy inhaling scents (rose, eucalyptus, clove, lemon, garlic, coffee, spearmint, orange, cinnamon, lavender, rosemary, anise, peppermint, and ginger). The scents will be available at two concentrations (1x and 2x), and the participants will be asked to nasally inhale each scent for 10 seconds. The participants will be presented with the 1x sticks and asked to state if a smell is present and to correctly identify the odor. If an odor is not detected or correctly identified, the 2x concentration of the same odor will be added to the remaining lot of inhalant sticks.

C7q) Infant skinfolds: Skinfolds will be assessed 4 timepoints for the infant (2 weeks, 2 months, 6 months, and 12 months). Six skinfolds will be measured to represent AT distribution in order to compare to larger trials that do not have DXA. All measurements will be collected using standardized procedures to our laboratory. All skinfolds will be identified using anatomical landmarks and taken on the right side of the body using Lange calipers (Beta Technology, Santa Cruz, CA). Skinfolds will be taken in order from head to toe and then repeated in that same order. If two skinfold measurements differ by more than 1 mm, a third measurement will be taken. The two measurements within 1 mm will be averaged and used for analysis. Biceps and triceps skinfolds will be measured at the midline of the anterior and posterior surface of the arm, respectively, on the mid-point between acromial process of the scapula and olecranon process of the ulna. Subscapular skinfold will be measured at the lower angle of the scapula. Suprailiac skinfold will be measured anteriorly to the midaxillary line and superiorly to the iliac crest, along the natural cleavage of the skin. The thigh skinfold will be measured at the mid-point between patella (knee cap) and inguinal crease at the anterior surface of the thigh. Flank skinfold will be measured immediately above the iliac crest at the mid-axillary line. Central FM will be calculated by adding the subscapular, suprailiac and flank skinfolds and dividing by three. Peripheral FM will be calculated by adding the thigh, biceps and triceps skinfolds and dividing by three.

C7r) Maternal urine & pregnancy test: Urine will be collected at all 6 maternal timepoints. Prior to maternal DXA at all post-partum visits (2 weeks, 2 months, 6 months, and 12 months), the urine will be used to perform a pregnancy test. Urine will be collected and aliquoted into 10, 2-mL cryovials and stored at -80°C. Urine will be used to test for polyfluoroalkyl substances. Unused samples will be banked for future evaluations related to nutrition and brain health at KUMC.

C7t) Breastmilk analysis: Participants who choose to breast feed will be asked to pump one breast until empty, homogenize the breastmilk by stirring, and return 20-mL to the study team for nutrient analysis. Participants will be asked to do this at 1 month, 2 months, 3 months, 4 months, 5 months, and 6 months, freeze it, and return it to the study team at the 2-month and 6-month visits. The remainder of the breastmilk collected can be kept by the participant and fed to their infant. Any leftover sample after initial nutrient analysis will be banked for future evaluations related to nutrition and brain health and KUMC.

C8) Steps to maximize adherence and retention: We will be using incentives for study visits, incentives for reporting goals, and regular short-term performance and feedback.

C8a) Incentive system: Participants will be compensated \$100 for each of the 6 study visits: baseline, end intervention, 2 weeks postpartum, 2 months postpartum, 6 months postpartum, and 12 months postpartum totaling up to \$600 for completion of all visits. Participants asked to return for repeat infant DXA (no more than 2 at each study timepoint) will be compensated an additional \$50. Compensation will be provided on a ClinCard, which is given at enrollment. After each visit study staff will load their unique card number with the respective pay. Participants can use the card anywhere Mastercard is accepted, and study staff does not have access to where the money will be spent.

C8c) Monitoring retention: When participants miss a session or reporting of behaviors, they will be contacted and a standardized protocol according to attendance and adherence demands will be used to make every effort to retain the participant or encourage reporting. This will be documented and used for program evaluation.

C9) Statistical analysis: The purpose of this study is to attain feasibility data therefore the small sample size does not afford the power to detect significance but to identify promising trends and relationships.

Analysis for Aim 1 H1: A t-test will be used to determine if there is a difference in maternal weight gain and fat accretion between the two groups.

Analysis for Aim 2 H2: A t-test will be used to quantify if there is a difference in fiber intake and dietary quality between the two groups.

Analysis for secondary Aim 1 H1: Repeated measures ANCOVA will be used to assess the difference in gut microbiome composition and diversity from baseline to study end between groups.

Analysis for secondary Aim 2 H2: A t-test will be used to determine if there is a difference in infant fat accrual between groups.

Analysis for secondary Aim 3 H3: A t-test will be used to determine if there is a difference in metabolic, inflammatory, and brain health markers.

Process evaluation: A process evaluation will be completed.

C10) Study challenges: A primary study challenge is the recruitment and retention. [name] has completed protocols successfully recruiting participants from the OB clinics at KUMC. [name], KUMC head of OBGYN, reports 1800 annual deliveries take place at KUMC with ~40% overweight. A second challenge is to assure the fidelity of the interventions. [name] will listen to 20% of GBPC sessions and compare the content delivered to a standardized checklist. If less than 80% of content is covered, [name] will re-train the Dietitian. A third challenge is to ensure subjects are attending sessions and reporting behaviors. We had a high degree of weekly reporting in our pilot study and anticipate a similar response rate in this pilot.

C11) Expected results: We anticipate the Hfib intervention will successfully prevent excessive GWG. The Hfib intervention holds promise to be delivered in routine clinical care. If the results are positive, the next study would be to adapt and embed the Hfib intervention in routine clinical care. The literature supports preventing excessive GWG has a high likelihood to greatly improve the health of both mothers and their offspring however there is variable success in published interventions. This supports the need to design and test interventions informed by prior study failures.

C12) Environment: The environment at KUMC is well suited to conduct this research.

References:

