The benefits of a HFib diet are supported extensively in the literature. Fiber protects against increasing body weight³⁰⁻³³, promotes fat loss³⁴⁻³⁹, increases satiety⁴⁰, and improves the metabolic and inflammatory profiles^{30,41-47}. Evidence that a HFib diet can reduce body weight and fat mass independent of a reduction in energy intake was highlighted in a recent meta-analysis⁴⁸ and a RCT in adults with MetS^{49,50}. The effect is hypothesized in part to be mediated through the powerful prebiotic effect of fiber that favorably shifts the gut microbiota leading to reduced weight gain⁴⁸, inflammation⁵¹, improved metabolic profile⁵¹, and prevention of fat accrual^{34-37,51}. Our working hypothesis is that consuming a HFib diet (≥ 30 g/day) will reduce GWG and fat accretion by diluting energy density, reducing hunger thereby reducing energy intake, and changing the gut bacteria composition. Our pilot data (n=20) found a 12 wk HFib pregnancy intervention reduced Firmicutes and increased Bacteroidetes, which was associated with reduced weight gain and fat accretion⁵². Current fiber intake of pregnant women is 17.3 g/day⁵³, well below the recommended intake (28 g/day⁵⁴), and triggering fiber to be classified as a nutrient of concern⁵⁵. Thus, increasing fiber intake has high potential for impact. However, RCTs in pregnant women are lacking to understand if this is an effective intervention strategy.

The project objective is to block randomize n=56 pregnant women to either a HFib diet or usual care. Eighteen weekly lessons will educate women on eating a HFib diet. To ensure fiber intake is met, daily snacks (10-12 g/day) will be provided. Weight gain, fat accretion, and stool microbiota will be measured twice during pregnancy (pre- and post-intervention) and assessed at 2 months, 6 months, and 12 months postpartum. Infant body composition will be measured at 2 weeks, 2 months, 6 months, and 12 months. The aims are:

Primary Aim 1: Assess the between group difference in maternal weight gain and fat accretion. H1: The HFib group will gain less weight and accrue less fat mass when compared to the control group.

Primary Aim 2: Compare fiber intake and dietary quality between groups. H2: The HFib group will consume more fiber and have a higher diet quality during pregnancy and postpartum.

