C2) Population to be studied: Women between 9 to 19 weeks pregnant with a BMI 18.5 – 45.0 kg/m² and between the ages of 18-45 years will be recruited from the University of Kansas Medical Center (KUMC) OB clinics. We will enroll all race/ethnic groups. Participant's routine OB care will be managed by their primary Obstetrician. Any interventions, laboratory or other evaluations, and decisions regarding delivery will be made by the primary Obstetrician. Groups of 6-10 subjects will be block randomized to control or the intervention group to ensure adequate size for optimal group dynamics. The intervention will start at 12-20 wks and last 18 weeks, ensuring intervention completion by 38 weeks in pregnancy. We will screen women to determine the current dietary fiber intake. If they are consuming 25 g/day of fiber or more, they will be excluded from the study. Women who do not have internet and phone access will be excluded from the study. Participants must be willing to consume provided snacks. Participants will also be excluded if they have history of gestational diabetes (GDM), diabetes, pre-eclampsia, hypertension, heart disease, hypothyroidism, or other metabolic abnormalities, current hyperemesis gravidarum, eating disorder, smoking, or are pregnant with multiples. Women that develop any of these medical conditions during pregnancy will be accounted for in the final analysis. Deviations from inclusion criteria will be at the discretion of the PI.

C3) Recruitment: We have access to the electronic clinic schedule, therefore we have the exact date and time of the recruit's OB visit. We have worked directly with physicians and staff providing an in service at meetings to ensure a smooth recruiting process so that we do not impede clinic flow. Annually, 1800 women are managed in the OB clinics at KUMC. Additionally, we will recruit using an electronic flyer via social media. Individuals who have agreed to future contact from previous studies will also be approached if eligible via email or phone.

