C4) Curriculum development: The interventions were designed based on the theoretical framework of the social cognitive theory (SCT)¹⁰². Bandura proposed that people attain and then maintain patterns of behavior and that behavior is based on the interaction of personal, environmental and behavioral factors. The consistency of behavior provides the foundation for development of our intervention strategy. Within the SCT there are several constructs that are directly related to weight control programs^{103,104}. **Table 2** provides examples of the constructs and behavioral strategies and examples of how these will be used in the study.

Table 2. Behavioral strategies used within the study

Behavioral Strategy	Examples of how used within the study
---------------------	---------------------------------------

Behavior Shaping	Participants are taught to modify their fiber intake according to recommendations.
Goal Setting	The Dietitian teaches sensible goal setting and assists participants to set personalized goals (e.g., fiber intake) to achieve appropriate GWG.
Self-Monitoring	Participants will report their body weight and fiber intake weekly & be taught self-monitoring.
Feedback & Reinforcement	Participants receive weekly feedback that includes reinforcement & strategies to overcome barriers.
Social/Peer Support	Group sessions provide peer support and interaction to model and teach behaviors.
Stimulus Control	Lessons provide coping & behavioral strategies to decrease cues for undesirable behaviors and to increase those for healthy behaviors.
Relapse Prevention	The Dietitian facilitates the development of a contingency plan to address high risk situations based on Marlatt and Gordon's relapse prevention model¹⁰⁵

C5) General intervention description: Group video conferencing will be used to deliver the intervention. The weekly 60-minute lessons for the Hfib group provide information on how to obtain ≥ 30 g/day of fiber (details below).

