C5a) General layout of the group sessions: The session will start with a review of the prior week's goals, with support and encouragement from group members and the Dietitian (5-10 minutes). A group discussion will occur with group members relating and/or providing personal insight and support. The Dietitian will lead discussion and engage the women by asking opened ended questions, providing encouragement and troubleshooting as needed. Each week there will be a structured lesson with an assignment to be completed after the session (20-30 minutes). The last 10-20 minutes of the session will be devoted to goal setting, discussion, questions, and wrap-up. For best group dynamics on video, 5-10 women are optimal.

C5b) Video System: Group sessions will be conducted using Zoom video conferencing system (Zoom Video Communications, Inc., San Jose, CA). Participants will be given a link with a password and instructed to call in 5 minutes prior to group start. A log will be generated to track attendance. All conference calls will be recorded for quality assurance and to serve as additional training for the group leader.

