This study will enroll pregnant women and their offspring. This study will block randomize 6-10 women into one of the following groups: a high fiber dietary intervention or UC. The primary aim is to assess the difference in maternal weight gain and fat accrual. All subjects will be given a body weight scale and report weekly their body weight. This allows close supervision of progression of each participant to ensure the intervention is not overly effective and all women are gaining adequate body weight. If a woman gains or loses more than 5 pounds over a two-week period, she will be contacted and her diet habits and fiber intake will be reviewed. Additionally, she will be asked if she is willing to provide her Obstetrician contact information and would like us to contact her Obstetrician. If so, a report will be sent to her Obstetrician. Infant growth will be charted and marked for review if crossing of two or more major percentile lines occurs. During pregnancy, maternal diet and body composition will be measured. A maternal DXA scan will be obtained at 2 weeks, 2 months, 6 months, and 12 months postpartum. Infant birth characteristics will be extracted from the electronic medical record. Infant body weight and body composition will be measured at 2 weeks, 2 months, 6 months, and 12 months using the Pea Pod. An infant DXA scan will be obtained at 2 weeks, 6 months, and 12 months.

RISKS TO HUMAN SUBJECTS

Human Subjects Involvement, Characteristics, and Design

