The women will be informed that the purpose of the study is to determine if a high fiber diet can help them gain the right amount of weight during pregnancy and that they will be placed in an intervention or control group. They will be told that if they participate in the study, regardless of their group assignment, that they will need to be seen two times during their pregnancy and four times after pregnancy. Further, they will be told if they are randomized to the intervention group they will be required to attend weekly video calls and report goals weekly to the study coordinator for 18 weeks.

Consent forms and HIPPA disclosure information per IRBs will be given to all subjects and their signatures witnessed. The consent forms will include a description of the study, nature of the data collection, the potential benefits and adverse reactions anticipated. Women will be assigned to group by random assignment provided by study statistician. The subjects will be told that their usual care would not be changed, withdrawn, or reduced if they chose to withdraw from the study at any time. The research team personnel will abide by all tenets of the University confidentiality policies, as well as the Privacy Protection for Research Subjects. All research staff will remain current in their NIH required Human Subjects protection and HIPAA certification.

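### The unit of randomisation is not settled, and no planned arm comparison allows for HFib women sharing session groups; standard errors are too small if outcomes within a group are positively correlated

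*Combined protocol and SAP*

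**What the plan says.** **Unit of randomisation.** Section C2 states: "Groups of 6-10 subjects will be block randomized to control or the intervention group to ensure adequate size for optimal group dynamics". The Specific Aims state: "The project objective is to block randomize n=56 pregnant women to either a HFib diet or usual care". The Protection of Human Subjects section has: "This study will block randomize 6-10 women into one of the following groups: a high fiber dietary intervention or UC". The consent text under Adequacy of Protection Against Risks has: "Women will be assigned to group by random assignment provided by study statistician", and adds that "if they are randomized to the intervention group they will be required to attend weekly video calls". No section states the allocation ratio.

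**Delivery.** HFib women attend 18 weekly 60-minute video sessions (C5c). Table 2 lists social support as a working part of the intervention: "Group sessions provide peer support and interaction to model and teach behaviors". C5a adds: "For best group dynamics on video, 5-10 women are optimal". Usual-care women receive standard obstetric care and report weight weekly, with no sessions (C5e).

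**Analysis.** C9 plans t-tests for both primary aims and for secondary Aims 2 and 3, and a repeated measures ANCOVA for secondary Aim 1. None names a session-group term, and no ICC appears. C9 says the trial is for feasibility and is not powered for significance; its comparisons are meant to pick out promising trends.

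**The concern.** The statements about allocation lead to different analyses. If women are randomised individually, the woman is the unit, but HFib outcomes may still be correlated within session group because the design has those women meet weekly and influence one another. If intact groups are allocated, the group is the randomised unit and there are only a handful of them.

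An ordinary t-test treats all women as independent. Positive correlation within HFib groups makes its standard error too small and its interval too narrow. In a trial meant to identify promising signals, a chance difference would then look more convincing than it is. C9 sets no alpha and no go/no-go rule, so no formal decision is corrupted. What is at stake is how far the reported intervals can be trusted.

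**Working it through.** **The plan's own figures.** N=56 has no calculation behind it, so there is nothing to reproduce. The one test result in the documents is the pilot comparison in Table 1 (18.4 ± 7.3 kg, n=9; 11.8 ± 4.0 kg, n=14). A pooled t-test on those figures gives p=0.0105, matching the stated 0.010.

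**Reading the allocation statements together**
- C2: groups of 6-10 go to an arm, and the reason given is group size. Natural reading: whole groups.
- Specific Aims and consent text: women are randomised. Natural reading: individuals.
- Protection of Human Subjects: fits either, since 6-10 could be a block size.
- Treating 6-10 as a 1:1 block does not resolve this. Such a block yields 3-5 HFib women, at or below the 5-10 that C5a calls best.

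**Inputs.** From the documents: 56 women; groups of 6-10 (C2) or 5-10 (C5a); pilot SDs 4.0 and 7.3 kg. Assumed: 28 per arm, two-sided 5%, fixed session groups, ICC 0.01-0.10.

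**Number of HFib groups.** Groups of 6-10: 28/10 = 2.8 and 28/6 = 4.7, so 3 to 5. If 1:1 blocks of 6-10 run as cohorts, groups hold 3-5 women: 28/5 = 5.6 and 28/3 = 9.3, so about 6 to 9.

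**Standard error, correlation in HFib only.** Design effect DE = 1 + (m − 1) × ICC, where m is group size. With equal SDs, true SE / t-test SE = √((DE + 1)/2).
- m=6, ICC 0.05: DE = 1.25, ratio √1.125 = 1.06.
- m=10, ICC 0.05: DE = 1.45, ratio √1.225 = 1.11.
- m=10, ICC 0.10: DE = 1.90, ratio √1.45 = 1.20.

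With the pilot SDs the correlated arm is the less variable one, so the ratio is √((4.0² × DE + 7.3²)/(4.0² + 7.3²)). At m=10, ICC 0.10: √((30.4 + 53.3)/69.3) = 1.10, not 1.20.

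**True error of the nominal 5% t-test, by simulation, correlation in HFib only**

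| Setting | ICC 0.01 | ICC 0.05 | ICC 0.10 |
|---|---|---|---|
| 3-5 HFib groups, equal SDs | about 5.1-5.5% | 6.3-7.5% | 7.7-10.1% |
| 6-9 HFib groups of 3-5, equal SDs | about 5.1% | 5.7-6.3% | 6.1-7.2% |
| 3-5 HFib groups, pilot GWG SDs | about 5.3-5.4% | 5.7-6.3% | 6.5-7.5% |

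At ICC 0 with equal SDs the t-test holds its 5% level.

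**If whole groups are allocated.** 56/10 = 5.6 and 56/6 = 9.3 give about 6 to 9 groups, so a group-level comparison has 4 to 7 degrees of freedom (groups minus 2), not 54. The critical t is 2.78 at 4 df and 2.36 at 7 df, against 2.00 at 54. With correlation in HFib only, woman-level t-test error is 5.2-9.9% over ICC 0.01-0.10. With ICC 0.10 in both arms it is about 11-15%.

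**Cost in precision.** Pooled pilot SD = √((8 × 7.3² + 13 × 4.0²)/21) = 5.50 kg. T-test half-width = 2.005 × 5.50 × √(2/28) = 2.94 kg. Under individual randomisation a partially nested interval is 8-57% wider with 3-5 HFib groups: 2.94 × 1.08 = 3.2 kg to 2.94 × 1.57 = 4.6 kg.

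**The case against.** The strongest case against acting is that the effect may be negligible. No ICC is known. Snacks and dietitian calls reach women individually (C5c), so a low ICC is plausible, and at 0.01 the excess error is at most half a percentage point. More and smaller groups, or the pilot's unequal SDs, shrink it further. C9 also disclaims significance. All of this stands and limits the size of the point. It does not remove it: the allocation statements still conflict, the design itself gives a reason for correlation in one arm, and low power does not excuse intervals that are too narrow.

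A reader might go further and infer that this is a cluster-randomised trial with a t-test error of 11-15%. The documents do not support that. Two statements speak of randomising women, and the 11-15% needs an ICC of 0.10 in usual care as well, where women never meet. Nor can a reader conclude that the sample size is wrong, since no power figure is claimed.

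A reader might also want a difference called promising only if it is significant both in the t-test and after adjustment. That is too costly here. For an assumed 0.75 SD effect it cuts power from about 79% to 63%, 68% and about 70% with 3, 4 and 5 HFib groups, even at ICC 0, where the t-test is valid.

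**Conclusion.** The point holds: the unit and ratio of randomisation are not settled, and no planned comparison allows for session groups. That standard errors are too small is conditional on a positive ICC.

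Under individual randomisation the consequence is small to moderate, with true error between about 5.1% and 10.1% across the settings tabulated. The upper end needs ICC 0.10, only three HFib groups and equal SDs. If whole groups are allocated, the woman-level t-test is the wrong primary analysis whatever the ICC, because women are not the randomised units.

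The figures rest on 28 per arm, two-sided 5%, fixed session groups, an assumed ICC and a single continuous outcome. The pilot-SD case covers GWG only and comes from 23 women. The repeated measures ANCOVA was not simulated. This is a cheap improvement, not a flaw that invalidates the trial.

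**What to change.** 1. Reconcile C2, the Specific Aims, the Protection of Human Subjects section and the consent text. State the unit of randomisation, the ratio and the block size.
2. Record each HFib woman's session group and any change of group. C5b already plans attendance tracking ("A log will be generated to track attendance"), so this adds one variable.
3. If women are randomised individually, keep each t-test and report beside it, as a sensitivity analysis, a partially nested interval: a random session-group effect in HFib only, with Satterthwaite or Kenward-Roger degrees of freedom. Add no joint significance rule. For secondary Aim 1, do this for alpha diversity and other single continuous measures only; the model is not directly defined for beta diversity.
4. If whole groups are allocated, make a group-level analysis primary: group means, or a mixed model with group-level degrees of freedom.
5. Report the ICC with its interval and say that it is imprecise. With 4 groups of 7 and a true ICC of 0.05, the median 95% interval runs from −0.11 to 0.68.

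**Cost.** Wording and one recorded variable. Besides being wider, the adjusted interval can be conservative at low ICC: with the group variance truncated at zero, error is 3.5-3.8% at ICC 0.01. That is why the t-test stays alongside. If whole groups are allocated, group-level intervals are 16-55% wider than the t-test's with correlation in HFib only, and 17-78% wider with correlation in both arms.
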